## **12.0 Statistical Considerations**

Based on a prior study performed in the lab with a similar paradigm using cTBS (Mirdamadi & [name], 2021), we predict an effect size  $f$  of at least 0.14 to detect a significant interaction in the planned mixed measures ANOVA between stimulation type (DLPFC, SMG, sham), motor training duration (short, long) and timepoint on the proprioception function and motor skill function. Power analysis indicates we need 24 subjects in each group to have 0.8 power to detect this effect (alpha 0.05).

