## 2.0 Objective(s)

The aim of the present study is to test role of activity in SMG and DLPFC in proprioception and motor skill learning. A robust way to identify whether a brain region plays a role in a behavior is to temporarily modulate its excitability in healthy people using non-invasive brain stimulation

(Cohen et al., 1997; Reis et al., 2008). This is commonly done in research with a short sequence of low-intensity transcranial magnetic stimulation (TMS), also known as repetitive TMS (rTMS). A small, temporary reduction in cortical excitability can be achieved through continuous theta burst stimulation (cTBS), a low intensity patterned form of rTMS that is delivered over 40 seconds, with excitability effects lasting up to an hour (Huang et al., 2005). rTMS is used clinically to treat conditions such as depression and is considered very low risk provided the generally accepted screening criteria are met. In the research setting, this technique is widely used not only in healthy adults (as in this study) but also in children and people with concussion, stroke, Parkinson's disease, and more (Rossi et al. 2021).

In separate groups of subjects, we will use a 40-second sequence of rTMS called continuous theta burst stimulation (cTBS) over SMG, DLPFC, or sham (control), before the subject performs tasks known to involve proprioception and either a short or longer sequence of motor skill learning (a maze tracing task). If cTBS over SMG or DLPFC has an impact on task performance for that group (in comparison to the sham, or control group), it suggests activity in that brain region is important for the affected aspect of task performance.

This project has two objectives:

- Objective 1. To explore the role of DLPFC and SMG in proprioception.
- Objective 2. To assess the role of DLPFC and SMG on motor skill learning and proprioceptive changes at two different time scales.

[figure not shown]
Because cTBS is intended to be disruptive, it is possible that the sham group will have the best performance in one or more outcome measures. It is also possible that some aspects of performance will be better in the SMG or DLPFC group due to complexities of the neural networks supporting these behaviors. However, it is not the goal of the study to determine which intervention yields the “best” task performance, it is simply to determine the details of how the DLPFC and SMG groups differ from each other and from the sham group.

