### 3.0 Outcome Measures/Endpoints

Outcome measures will be assessed during the main (experimental) session, which takes place on a single day. Proprioceptive outcome measures will be assessed 3 times, and motor outcome measures 4 times, on this day (Fig. 1).

Outcome Measure 1: Proprioception. This will be quantified from a psychometric function, based on a sequence of trials in which the participant estimates their hand position. From the psychometric function we will extract proprioceptive bias (50% point) and sensitivity (distance between 25% and 75% points on the function).

Outcome Measure 2: Motor skill. This will be quantified from the speed-accuracy function, based on the person's in-track accuracy when tracing the maze at three different speeds. Shifts in the speed accuracy function (better accuracy at any of the movement speeds) indicates motor skill learning.

**Fig. 1.** Session design of the main (experimental) session, which takes place on a single day. Proprioception and motor skill will be assessed at multiple time points.

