Figure 2. Setup for behavioral procedures. Participant holds handle of robotic manipulandum with right hand and makes arm movements to targets presented in visual display (motor skill task) or judges where handle is moved in relation to a target (position sense task).

primary motor cortex with TMS (Caulfield et al., 2022; Nieminen et al., 2022). The main session includes all the same elements as the familiarization session (TMS, proprioceptive assessment, motor skill task), plus cTBS. After the first motor skill assessment and proprioception assessment (Fig. 1), we will deliver single pulses of magnetic stimuli over the motor cortex and determine the resting motor threshold (RMT) as the lowest TMS intensity that elicits a muscle twitch of at least 50 microvolts at least 10 times out of 20 (Rossini et al., 2015). We will then deliver cTBS in the standard pattern (600 pulses over 40 seconds, at an intensity of 70% of RMT). For non-sham groups the coil will be positioned over DLPFC or SMG, as determined by the Brainsight neuronavigation system. For sham groups, the coil will be tilted 90 degrees so the magnetic field is not directed into the head; they hear the clicking noises but no current is induced in the brain (Rossi et al., 2009). Then, subjects will perform second pair of assessment tasks. This will be followed by practice of the maze tracing task for about 20 minutes, with a motor skill assessment partway through. Practice of the maze task will occur at a single MT range (MT 2). The session will conclude with the third pair of assessment tasks.

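### Section 12.0 names one interaction and ties no test to Objective 1; a planned, baseline-adjusted comparison at the assessment after cTBS and before practice would supply it

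*Combined protocol and SAP*

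**What the plan says.** Section 2.0 sets two aims. The first reads "Objective 1. To explore the role of DLPFC and SMG in proprioception" and involves no training duration. The second concerns motor skill learning and proprioceptive change at two time scales. The same section says that a difference from sham would implicate a region, but gives no test or timepoint for that comparison. It describes cTBS as a brief stimulation "with excitability effects lasting up to an hour".

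Section 3.0 states: "Proprioceptive outcome measures will be assessed 3 times, and motor outcome measures 4 times, on this day". Section 7.0 gives the order in the main session. A first pair of assessments (motor skill and proprioception) precedes cTBS, and a second pair comes directly after it. Practice is next, described once for all subjects: "This will be followed by practice of the maze tracing task for about 20 minutes, with a motor skill assessment partway through". For the end of the visit the section says: "The session will conclude with the third pair of assessment tasks". Proprioception is therefore measured before cTBS (pair 1), after cTBS but before the practice block (pair 2), and after practice (pair 3).

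Section 12.0 is the whole analysis plan. Its one named target is the interaction "to detect a significant interaction in the planned mixed measures ANOVA between stimulation type (DLPFC, SMG, sham), motor training duration (short, long) and timepoint", for both the proprioception and the motor skill function. It adds: "Power analysis indicates we need 24 subjects in each group to have 0.8 power to detect this effect (alpha 0.05".

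**The concern.** Pair 2 is the only proprioception assessment that follows cTBS and precedes the practice block, so it bears most directly on Objective 1. At that point short and long training cannot yet differ, so a direct effect of stimulation there should be the same in both. An interaction that involves training duration looks only for effects that differ between durations.

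If the reader falls back on stimulation x timepoint, a significant result could be an early effect that fades or one that appears only after practice. The first bears on Objective 1 and the second on Objective 2. With no contrast named, the deciding timepoint would be chosen after the data are seen.

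Pair 3 is also the latest measurement, so practice and time since cTBS change together.

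**Working it through.** **Inputs.** From Section 12.0: f = 0.14, alpha 0.05, power 0.8, 24 per group. From Section 6.0: three groups, hence 3 x 24 = 72. From Section 3.0: three proprioception timepoints. Assumed, because the documents do not give them: equal correlation rho between timepoints (0.5, range 0.3 to 0.7), sphericity, and f = 0.14 applied to stimulation x timepoint.

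**The plan's own figure.** For a group x time test, lambda = f² x N x m/(1 - rho), with (k - 1)(m - 1) and (N - k)(m - 1) degrees of freedom.
- Six groups, m = 3, rho = 0.5: N = 143 is needed, that is 24 per group. Power at 144 is 0.804. This is a pooled 10-df test, not the 4-df three-way term.
- Three groups, m = 3, rho = 0.5: N = 104 is needed (35 per group); 72 gives 0.616.
- Three groups, m = 4, rho = 0.6: 72 gives 0.802.

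So 24 per group can be reproduced, but not in a way that shows which term was meant.

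**Three-way term.** Let one active group shift by d SD, with patterns over pairs 1, 2, 3. Take the 3 x 2 x 3 cell means with duration between subjects. The three-way effect is the short-long difference in the stimulation x timepoint effects.
- (0,d,0), (0,0,d) or (0,d,d), equal in both durations: three-way sum of squares 0; stimulation x timepoint 0.889 d² in each case.
- A pair 3 effect in long training only: three-way sum of squares 0.222 d².

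Simulated rejection by the three-way F for (0,d,0), with 12 per cell, was 4.6-5.2% over rho 0.3 to 0.7 and d from 0.59 to 0.90.

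**Effect size.** Lambda for stimulation x timepoint is 0.0196 x 72 x 3/(1 - rho) = 4.234/(1 - rho). For a shift in one group at one timepoint it is also 24 x (4/9) x d²/(1 - rho). Equating them, d² = 4.234/10.667 = 0.397 and d = 0.63.

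**Power at N = 72, rho = 0.5.**
- Stimulation x timepoint, F(4,138): lambda = 4.234/0.5 = 8.47, power 0.616 for (0,d,0), (0,0,d) and (0,d,d) alike.
- Change from pair 1 to pair 2, F(2,69): lambda = 24 x (2/3) x 0.397/(2 x 0.5) = 6.35, power 0.590 for (0,d,0).
- Pair 2 adjusted for pair 1, F(2,68): lambda = 24 x (2/3) x 0.397/(1 - 0.25) = 8.47, power 0.723 for (0,d,0), or 0.62 at alpha 0.025.
- One site against sham, adjusted, F(1,68): lambda = 12 x 0.397/0.75 = 6.35, power 0.70 at alpha 0.05 and 0.59 at 0.025.

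Both pair 2 omnibus comparisons reject at 0.05 for (0,0,d).

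**Sensitivity.** Over rho 0.3/0.5/0.7: stimulation x timepoint 0.459/0.616/0.856, change 0.446/0.590/0.821, adjusted 0.633/0.723/0.881. With f = 0.14 applied afresh to a two-timepoint change test, power is 0.40/0.54/0.77. With six cells of 24 (144 in total) and rho 0.5: 0.92, 0.90 and 0.96. The three-way term is still 0.

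**Timing.** Section 7.0 gives about 30 minutes for the two assessments at familiarization. If the main session is similar, and the mid-practice assessment falls inside the 20 minutes, pair 3 starts 30 + 20 = 50 minutes after cTBS and ends at 2 x 30 + 20 = 80. Section 2.0 puts the limit of the excitability effect at an hour.

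**What stays confounded.** The pair 3 difference is d x (1 - share faded) + learning effect. No fade with no learning effect, half faded with 0.5d, and fully faded with d all give (0,d,d).

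**The case against.** Section 12.0 is a power statement, and it does not say that the three-way term is the only one to be read. A full factorial ANOVA contains stimulation x timepoint, and pair 2 is presumably a level of timepoint. The calculation that returns 24 per group at rho 0.5 with three timepoints is a pooled six-group x time test. With 144 subjects, that test has 80% power for the same pair 2 effect (d = 0.63). All of this stands. A reader might infer that the plan can detect an Objective 1 effect only 5% of the time, or that pair 2 goes unused. The documents support neither. The 5% belongs to one reading, though the natural one, and what is missing is a specified contrast.

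The three-way result also needs duration to be a between-subject factor, which the documents leave open. Section 6.0 has three groups that differ in both stimulation and amount of practice, Section 7.0 describes one practice period for all, and Section 12.0 has a short/long factor. If duration is not between subjects, the three-way term cannot be estimated for proprioception, which has no mid-practice assessment. The objection stands against the 5% figure, but it leaves Objective 1 no better served.

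Pair 2 is not free of practice. It follows familiarization and the 30 maze trials of the first motor assessment (10 in each of three speed ranges), and its own motor assessment is 30 more. That limits what pair 2 shows and should be stated.

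Objective 1 is worded as exploratory, and Fig. 1 and the figure after the objectives are not shown; they may give times or link timepoints to objectives. Even an exploratory aim needs a test that responds to the effect and a stated timepoint.

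**Conclusion.** The point holds in this form: no test, contrast or power in Section 12.0 is tied to Objective 1. On the three-way reading with duration between subjects, the named test is blind to a cTBS effect that is equal in both durations. On looser readings it can respond, but stimulation x timepoint does not separate an effect only at pair 2 from one only at pair 3 (62% power for each). A baseline-adjusted pair 2 comparison does, at 72% against 5%, and 63-88% for a pair 2 effect over rho 0.3 to 0.7.

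The zero is exact. The powers rest on the assumed correlation, on 72 subjects, and on transferring f = 0.14 to stimulation x timepoint. This should be changed; it does not show that the study cannot answer Objective 1, since the measurements needed are already scheduled. Nor would the new contrast separate wash-out from learning at pair 3.

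**What to change.** In Section 12.0:

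1. Test Objective 1 with a planned comparison of second-pair proprioceptive bias and sensitivity, adjusted for the first-pair baseline. Compare each active site with sham, and state a multiplicity rule across the two sites and two measures. Use the change from the second pair to later assessments, by group, for Objective 2.
2. Record minutes since cTBS at each assessment and report them by group.
3. State that when a group difference is present at pair 2, its persistence or shrinkage by pair 3 cannot be divided between wash-out and learning. State also that pair 2 precedes the practice block but not all task exposure.
4. Reconcile Sections 6.0, 7.0 and 12.0 on the number of groups and on whether training duration is a between-subject factor.

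Stimulation and task order do not change. The cost is wording, one time stamp per assessment, and a few planned tests with a multiplicity price: at alpha 0.025 the adjusted omnibus comparison falls from 72% to 62%, and one site against sham from 70% to 59%. The conclusion for Objective 2 becomes more cautious.

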## 5.0 Study Design

## 6.0 Enrollment/Randomization

Potential subjects will initiate contact with the research staff in response to the recruitment flyers. The subject will be given information about what the experiment entails and will be asked questions to make sure they meet the inclusion/exclusion criteria. If they are interested in participating and meet the inclusion/exclusion criteria, then they will be scheduled for their first session (familiarization session) which will take place in the Sensorimotor Neurophysiology Laboratory, [name].

At the familiarization session, before any experimental procedures occur, a research team member will explain the procedures in more detail and go through the consent form with the subject. The subject will then have the opportunity to ask any questions and read the informed consent before signing. After the familiarization session, if the subject was not bothered by TMS and wants to continue, random group assignment will occur, following a block randomization table. There will be 3 groups that differ in cTBS intervention and amount of motor skill practice. Subjects will have a 67% chance of receiving cTBS, and a 33% chance of receiving sham cTBS (details below).

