## 7.0 Study Procedures

All procedures are conducted for research purposes only. The study will be comprised of a familiarization session, an anatomical MRI brain scan session (except for those assigned to a sham group) and one experimental session. Subjects will be offered the option to combine their familiarization session and MRI scan or MRI scan and experimental session in the same day for a total of 2 lab visits or on separate days for a total of 3 lab visits. (Table 1). All study procedures will take place in the Sensorimotor Neurophysiology Lab, SPH 079 and the MRI scan will take place in the Imaging Research Facility in the Psychology building.

**Table 1.** Study structure. TMS = transcranial magnetic stimulation, cTBS = continuous theta burst stimulation, MRI = Magnetic Resonance Imaging. TMS is applied over motor cortex. cTBS is applied over DLPFC or SMG.

Session	Procedures	Proceed to next session if...
Familiarization	TMS, motor skill task, proprioception assessment	Subject comfortable with TMS, can follow task instructions, and wants to continue
MRI anatomical scan	Anatomical scan of the brain – dependent on group assignment	Subject wants to continue
Main Session	TMS, cTBS, proprioception and motor skill assessments, motor skill practice.	End of experiment

The familiarization session involves transcranial magnetic stimulation (TMS) over the motor cortex, a motor skill task that involves a series of tracing movements with the right arm, and a position sense task that involves a series of judgements about the location of their right-hand position. First, subjects will fill out a TMS screening form. Upon confirming eligibility, subjects will sit in a comfortable chair while a non-invasive brain stimulation device (the TMS coil) is held over their head. We will deliver brief magnetic stimuli over the motor cortex that evoke a small twitch in their hand muscles. Subjects will wear a pair of goggles that enable accurate positioning of the TMS coil relative to the

head (Brainsight Neuronavigation system) and have stick-on sensors on their hand to measure their muscle activity upon stimulation. This will take approximately 20 minutes.

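### Adjusting for the same-session pre-cTBS value would cheaply sharpen post-cTBS group differences (variance 35% to 5% below change scores, for assumed correlations 0.3 to 0.9), but adds little to the named three-way interaction

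*Combined protocol and SAP*

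**What the plan says.** Section 12.0 is the whole analysis plan. It expects an effect size f of at least 0.14 for an interaction in the "planned mixed measures ANOVA between stimulation type (DLPFC, SMG, sham), motor training duration (short, long) and timepoint", and asks for 24 subjects per group for 0.8 power at alpha 0.05. It names no covariate, does not list the levels of timepoint, and gives no correlation between assessments.

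Section 3.0 sets the schedule for the main session: "Proprioceptive outcome measures will be assessed 3 times, and motor outcome measures 4 times, on this day". Section 7.0 fixes the order. "After the first motor skill assessment and proprioception assessment", the motor threshold is determined and cTBS is given, then a second pair of assessments follows. Practice comes only after that: "This will be followed by practice of the maze tracing task for about 20 minutes, with a motor skill assessment partway through". A third pair ends the session. Every subject who reaches cTBS therefore has a same-session, pre-stimulation value of both outcomes.

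Two other places matter. Section 6.0 puts random assignment after the familiarization session, so the main-session baseline is measured after assignment. Section 7.0 exempts sham subjects from the MRI, and says of the visits: "Subjects will be offered the option to combine their familiarization session and MRI scan or MRI scan and experimental session in the same day".

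**The concern.** When a pre-treatment value of the outcome is available, a group-by-time comparison that includes it as a repeated measure in effect subtracts it with a slope of 1. Regression adjustment estimates the slope instead, and is more precise whenever the correlation is below 1. With 24 per group that precision is worth having. It bears on the stimulation comparison just after cTBS, which is the direct test of Objective 1, and on the stimulation effect after practice, which is part of Objective 2. Leaving open how baseline enters also leaves a choice to be made after the data are seen.

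**Working it through.** **Inputs.** From Section 12.0: f = 0.14, alpha 0.05, power 0.8, 24 per group. From Section 3.0: three proprioception and four motor assessments, hence two and three after cTBS. Assumed, because the documents give neither: the correlation rho between assessments (0.3 to 0.9, equal for all pairs unless stated) and a shift of 0.5 SD. Variance is set to 1. Powers are from the noncentral F distribution.

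**1. The plan's own figure.** For a group-by-time test, lambda = f² × N × m / (1 − rho). With six cells of 24, m = 3 and rho = 0.5, lambda = 0.0196 × 144 × 3 / 0.5 = 16.93 on 10 and 276 df, and power is 0.804. So 24 per group reproduces, but only with an unstated rho. Three groups, four timepoints and rho = 0.6 also give it (power 0.802). The documents therefore do not fix rho.

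**2. Group difference at one post-cTBS assessment.** The variance per subject is 2(1 − rho) for change and 1 − rho² when adjusted. The ratio is (1 + rho)/2, a reduction of (1 − rho)/2. For a 0.5 SD shift in one of three groups of 24, lambda = 24 × (2/3) × 0.25 / v = 4/v, with df 2, 69 (change) and 2, 68 (adjusted).

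| rho | variance reduction | lambda, change | lambda, adjusted | power, change | power, adjusted |
|---|---|---|---|---|---|
| 0.3 | 35% | 2.86 | 4.40 | 0.30 | 0.43 |
| 0.5 | 25% | 4.00 | 5.33 | 0.40 | 0.51 |
| 0.7 | 15% | 6.67 | 7.84 | 0.61 | 0.69 |
| 0.8 | 10% | 10.00 | 11.11 | 0.80 | 0.84 |
| 0.9 | 5% | 20.00 | 21.05 | 0.98 | 0.99 |

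Estimating the slope from 72 subjects costs about one percentage point: 34/24/14/4% at rho 0.3/0.5/0.7/0.9.

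**3. The named three-way interaction.** Take six cells of 24 and a 0.5 SD effect at the final assessment only, in one stimulation type under one duration. With k post-cTBS assessments and d the vector of effects, lambda = (24/2) × (2/3) × d′V⁻¹d. For change V = (1 − rho)(I + J), and for the adjusted analysis V = (1 − rho)(I + rho·J), where J is all ones. At rho = 0.5:

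- Proprioception (k = 2, 4 df): lambda 2.67 becomes 3.00, and power 0.216 becomes 0.240.
- Motor skill (k = 3, 6 df): lambda 3.00 becomes 3.20, and power 0.203 becomes 0.215.

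Over rho 0.3 to 0.9 the power gain is 0.007 to 0.028 for proprioception and 0.004 to 0.015 for motor skill.

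**4. Change across practice.** With equal correlations, the final-minus-second difference is uncorrelated with the pre-cTBS value, so adjustment gains nothing. If correlation decays as AR(1), the reduction is rho²(1 − rho)/2. This peaks at rho = 2/3: (4/9) × (1/3) / 2 = 0.074, about 7%.

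**5. The cost if baseline is not comparable.** Suppose being in a non-sham arm shifts every assessment by delta. Change removes the shift; the adjusted contrast keeps (1 − rho) × delta. For an assumed 0.2 SD at rho = 0.5 the bias is 0.10 SD, lambda = 24 × (2/3) × 0.01 / 0.75 = 0.213, and the 2-df type I error is 0.066. At rho = 0.3 the figures are 0.14 SD and 0.076.

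**The case against.** The strongest reply is that baseline is probably used already. Timepoint is a factor and the first assessment precedes cTBS, so if that assessment is a level, group-by-time compares changes from it. This stands. A reader might infer that the plan ignores baseline or is invalid, and the documents do not support that. (If baseline were not a level, the comparator would be the post-cTBS value alone and the reduction would be rho², or 9% to 81% over the same range.)

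The second reply is that the 5% to 35% does not concern the test Section 12.0 names. This also stands, as step 3 shows. A reader might carry that percentage over to the three-way interaction, or expect a large rise from 0.804 at the stated f. A large rise needs a group effect already at the second assessment. Practice has not begun then, so such an effect cannot depend on training duration. If short and long mean the partway and final assessments, the duration part is a contrast between post-cTBS assessments and gains nothing under equal correlations.

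Third, adjustment carries its greatest risk of bias at low rho, where it also helps most. This is true for a shift that persists through the session. For a shift at baseline only, the adjusted analysis does better than change (type I error 0.066 against 0.099 at rho 0.5, 0.2 SD). Nothing in the documents shows that either shift occurs. The risk is a reason to keep the planned ANOVA alongside, not to forgo adjustment.

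**Conclusion.** A low-priority improvement to consider; the plan is not wrong on this point. Section 12.0 names no baseline covariate although a same-session pre-cTBS value of each outcome is collected. Adjustment makes stimulation-group differences at a post-cTBS assessment more precise: usefully at rho 0.3 to 0.7, slightly at 0.8 or above. It leaves the three-way interaction almost unchanged and does not help change across practice beyond about 7% in variance. All sizes rest on an assumed rho, a pre-to-post change comparator and, except for the AR(1) figure, equal correlations. The powers also rest on an assumed 0.5 SD effect. None of this supports reducing the sample size. The conflict between Section 6.0 ("There will be 3 groups that differ in cTBS intervention and amount of motor skill practice") and the 3 × 2 between-subject factors in Section 12.0 is a separate matter to be reconciled.

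**What to change.** In Section 12.0, state the levels of timepoint and add the following:

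- Estimate stimulation-group differences from a model of the post-cTBS assessments only. Fixed effects are stimulation type, timepoint, training duration (if two durations are run) and their interactions. Covariates are the pre-cTBS value of the same measure and its interaction with timepoint. Use an unstructured covariance across assessments.
- For motor skill, use one accuracy score per assessment, averaged over the three movement-time ranges, with the baseline averaged the same way. Report each range separately as supportive, because Section 3.0 says: "Shifts in the speed accuracy function (better accuracy at any of the movement speeds) indicates motor skill learning".
- Keep the contrast from the second to the final assessment for change across practice.
- Report pre-cTBS values by arm, and keep the planned mixed ANOVA as a sensitivity analysis.

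The cost is one degree of freedom per covariate term and a little more analysis, with no new data and no added burden on participants. The downside is the bias in step 5 if arm membership shifts scores throughout the session, for example through fatigue from a same-day MRI. The baseline report and the sensitivity analysis are there to reveal it.

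### Section 12 powers a stimulation × training duration × timepoint interaction that the three randomised groups of Section 6, read literally, cannot estimate, and total N could be 72 or 144

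*Combined protocol and SAP*

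**What the plan says.** Section 12 names one planned analysis, a mixed ANOVA testing an interaction "between stimulation type (DLPFC, SMG, sham), motor training duration (short, long) and timepoint on the proprioception function and motor skill function". It expects an effect size f of at least 0.14 and concludes: "Power analysis indicates we need 24 subjects in each group to have 0.8 power to detect this effect (alpha 0.05". It gives neither the number of groups nor a total N.

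On allocation, Section 6 states: "There will be 3 groups that differ in cTBS intervention and amount of motor skill practice". It adds: "Subjects will have a 67% chance of receiving cTBS, and a 33% chance of receiving sham cTBS".

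Section 7 describes the main session from cTBS to the last assessment. After the second pair of assessments: "This will be followed by practice of the maze tracing task for about 20 minutes, with a motor skill assessment partway through". Then: "The session will conclude with the third pair of assessment tasks". No short or long variant appears there.

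Other wording suggests more than three cells. Section 2 has participants do either a shorter or a longer amount of skill practice, and Objective 2 concerns two time scales for both motor skill and proprioception. Section 7 exempts some participants from the scan in these terms: "an anatomical MRI brain scan session (except for those assigned to a sham group) and one experimental session". It uses the plural again for the sham procedure: "For sham groups, the coil will be tilted 90 degrees so the magnetic field is not directed into the head". Section 3 sets three assessments for proprioception and four for motor skill.

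**The concern.** A three-way interaction asks whether the effect of training duration on change over time differs between stimulation types. To estimate it in full, each stimulation type must contain people on both durations. Three groups that cover three stimulation types, with one practice amount each, cannot supply this. If all three share one practice amount, duration is a constant, and Section 6 is also wrong to say that practice differs. If practice differs by group, duration is confounded with stimulation.

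This is the only analysis that the plan specifies and powers. The group structure fixes the block randomisation table, the recruitment target and the model. If it stays open, the model could end up being chosen after the data are seen. Objective 2 is also exposed: on a single schedule, proprioception is assessed only once after practice, so its part of the two-time-scale question has no answer.

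**Working it through.** **Inputs.** From Section 12: f = 0.14, alpha 0.05, power 0.80, 24 per group. From Section 6: three groups, about two thirds active. From Section 3: m = 3 timepoints (proprioception) or m = 4 (motor skill). Not in the supplied text, so assumed: within-subject correlation ρ = 0.5 (range 0.3 to 0.7) and sphericity.

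**Formula.** For a within-between interaction, power comes from the noncentral F distribution with λ = f²·N·m/(1 − ρ) and df2 = (N − cells)(m − 1). For a general test of k groups by timepoint, df1 = (k − 1)(m − 1). For the three-way term, df1 = (3 − 1)(2 − 1)(m − 1).

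**1. The plan's own figure.** Six groups of 24, m = 3, ρ = 0.5: λ = 0.0196 × 144 × 3/0.5 = 16.93. The general test has df 10 and 276 and power 0.804, which matches the stated 24 and 0.8. That is not the term Section 12 names. The three-way term (df 4 and 276) has power 0.923 in the same design, and falls to 0.80 at ρ of about 0.30.

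**2. Degrees of freedom for the powered term.** The full 3 × 2 × m model has 18 parameters (m = 3) or 24 (m = 4).

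| Layout | Rank, m = 3 | Rank, m = 4 | Three-way df |
|---|---|---|---|
| Six cells (24 or 12 per cell) | 18 of 18 | 24 of 24 | 4 or 6 |
| Three groups, one practice amount each (same or mixed) | 9 of 18 | 12 of 24 | 0 |

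The ranks of 9 and 12 equal 3 × 3 and 3 × 4, the size of a stimulation × timepoint model alone. Duration therefore adds nothing that can be estimated.

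**3. Total N.** Three layouts fit the 67%/33% split, because 2/3 = 4/6:
- six groups of 24: 6 × 24 = 144;
- three stimulation arms of 24, each split by duration: 6 × 12 = 72;
- three groups of 24 on one schedule: 3 × 24 = 72.

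**4. Power under each layout at f = 0.14.**

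| Layout and test | m | df | ρ = 0.3 | ρ = 0.5 | ρ = 0.7 | ρ giving 0.80 |
|---|---|---|---|---|---|---|
| 6 × 24, general group × timepoint | 3 | 10/276 | 0.626 | 0.804 | 0.972 | 0.495 |
| same | 4 | 15/414 | 0.701 | 0.871 | 0.990 | 0.417 |
| 6 × 24, three-way term | 3 | 4/276 | 0.798 | 0.923 | 0.995 | 0.303 |
| 6 × 12, three-way term | 3 | 4/132 | 0.458 | 0.615 | 0.856 | 0.658 |
| same | 4 | 6/198 | 0.519 | 0.691 | 0.915 | 0.599 |
| 3 × 24, stimulation × timepoint | 3 | 4/138 | 0.459 | 0.616 | 0.856 | 0.657 |
| same | 4 | 6/207 | 0.520 | 0.691 | 0.915 | 0.598 |

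The figure of 24 does not identify the design. It gives 0.80 for six groups at ρ of about 0.50 (general test, m = 3) or 0.30 (three-way term, m = 3), and for three groups at ρ of about 0.66 (m = 3) or 0.60 (m = 4).

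**5. Duration as a within-subject factor.** The mid-practice assessment could stand for short training and the final one for long. Duration would then be part of timepoint, with no separate three-way term. It could serve motor skill only, because Section 7 places no proprioceptive assessment partway through practice.

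**The case against.** The strongest reply is that the layout may be given where the supplied text is incomplete. Section 5 is a bare heading, Fig. 1 is not shown, and some Section 7 text before the main-session description is lost. Nothing can be held against the plan for those gaps. Two of the three layouts make the three-way term fully estimable, and the wording in Sections 2, 6 and 7 leans towards both durations being used. On that view the count of three in Section 6 is loose or out of date, and 0 df is a worst case. The power values also rest on a correlation that the supplied text does not give, and the match at six groups uses a pooled test in place of the named one.

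Most of this stands as a limit on the conclusion. The trial's actual layout is not known from this text, and the power table cannot show that the trial is underpowered. The conflict itself remains. The group count in Section 6 is intact text and does not fit the two crossed factors of Section 12. The Section 7 account from cTBS to the final assessments gives one practice period and no short/long split. Recovering the missing parts could settle the intent, but Section 6 would still need correction or clarification.

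**Conclusion.** The concern holds. Followed literally, the only test that the plan powers has 0 df, where it should have 4 or 6, and 24 per group can mean 72 or 144 participants. This part needs no assumption about correlation. Confidence is high for the conflict between Sections 6 and 12. The actual layout stays open because of the missing material.

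The power values are conditional on f = 0.14 carried unchanged across tests, on sphericity and on ρ. For the two N = 72 layouts they run from 0.46 to 0.92 over ρ of 0.3 to 0.7, which spans inadequate to adequate.

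Objective 1 survives, because the second pair of assessments comes after cTBS and before practice. Stimulation × timepoint stays testable if all groups share one schedule. On one schedule, the proprioceptive half of Objective 2 is lost. The point must be resolved before data are examined.

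**What to change.** The sponsor should say which design is meant and make Sections 2, 6, 7 and 12 agree. In every case, state the number of groups, total N, the exact term powered, and the correlation and sphericity assumed.

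- **(a) Six groups.** Change the group count in Section 6 to six (three stimulation types by two practice durations), describe both durations in Section 7, state N = 144, and keep the Section 12 model. Cost: wording only if 144 were already planned. If 72 were planned, recruitment doubles (144/72 = 2).
- **(b) Three stimulation arms of 24, each split by duration.** Say so in Section 6, describe both durations in Section 7, keep the Section 12 model, and restate power for 12 per cell. Cost: wording and a new power statement. At ρ = 0.5, 0.80 power for the three-way term would need 18 per cell (N = 108, three timepoints) or 15 per cell (N = 90, four). Twelve per cell is enough at ρ of about 0.66 or 0.60.
- **(c) Three groups on one schedule.** Replace the Section 12 model with stimulation × timepoint, remove the statement in Section 6 that practice amount differs, limit the two-time-scale claim in Objective 2 to motor skill, align the short/longer wording in Section 2, and restate power for N = 72. Cost: wording, a new power statement, and the loss of the two-time-scale claim for proprioception. At ρ = 0.5, 0.80 power would need 35 per group (N = 105, three timepoints) or 30 per group (N = 90, four). Twenty-four per group is enough at ρ of about 0.66 or 0.60.
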